**Scenario 3**

The one-sided type I error rate of Scenario 3 is bounded by the following inequality:

$$\begin{aligned}
 &P(\text{Reject } H_{01}, \text{Reject } H_{02}, \text{Reject } H_{03} | H_{11}, H_{12}, H_{03}) \\
 &\leq P(\text{Reject } H_{01}, \text{Reject } H_{03} | H_{11}, H_{12}, H_{03}) \\
 &= P(\text{Reject } H_{01}, \text{Reject } H_{03} | H_{11}, H_{03})
 \end{aligned}$$

Applying the same argument in Scenario 2 (with PFS replaced by ORR), the type I error rate can be protected by using one-sided significance level of 0.016 for the testing of secondary ORR endpoint at both the interim and final analyses.

#### Appendix 4. Formula and Sample Code to Compute Predictive Power

The predictive power at the futility interim analysis will be evaluated as

$$\Phi \left( \sqrt{\frac{d_1}{d-d_1}} \cdot Z_{\frac{\alpha}{2}} - \sqrt{\frac{d \cdot d_1}{4 \cdot (d-d_1)}} \cdot \log \hat{\lambda}_1 \right)$$

Where  $d_1$  is the number OS events observed by the time of futility interim analysis;  $d = 286$  is the number of OS events at the final analysis;  $\hat{\lambda}_1$  is the observed log HR (treatment arm vs. placebo) at futility interim;  $\alpha = 0.05$  is the Type I error of the final analysis;  $\Phi(\cdot)$  is the probability function of standard normal distribution;  $Z$  is the inverse of  $\Phi$ .

Sample SAS code:

```
/*count number of death events observed by futility interim analysis
d1*/
proc sql;
    select Count(distinct(a.subjid)) into: d1
    from eff_strat_1 as a
    where a.cnsr_os=0; /* cnsr_os=0 denotes death events*/

quit;

/*compute hazard ratio adjusted by stratification factor*/
ods output HazardRatios=os strat_1;
proc phreg data=eff_strat_1;
    class cohort;
    model os*cnsr_os(1)=cohort; /* cnsr_os=1 denotes censored*/
    strata strata;
    hazardratio cohort/diff=ref alpha=0.05;
run;

/*compute predictive power*/
data HR_PP_1;
    set os_strat_1;
    /*assume HazardRatio is treatment arm vs. placebo. Otherwise,
invert the Hazard ratio for PP calculation*/
    Z=sqrt(&d1/(286-&d1))*quantile("normal", 0.025) -
sqrt(286*&d1/4/(286-&d1))*log(HazardRatio);
    PP=cdf("normal", z);
run;
```

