**Table 8-1. Stopping Boundaries for Efficacy Analyses**

Efficacy Analysis	Events (%)	Stopping Boundary	
		Z scale	One-sided p-value scale
Interim	191 (66.7%)	2.509	0.006
Final	286 (100%)	1.993	0.023

Given significance of OS at either the interim or final analysis, the secondary endpoints of PFS and ORR will sequentially tested at the 1-sided 0.016 significance level.

If the DMC sees substantial evidence of benefit of the GS-5745 + mFOLFOX6 combination, (ie, OS is significantly better in Arm A compared to Arm B), Gilead personnel who are not involved with the study may perform an unblinded review of the integrated interim data, and may decide to stop the study and offer GS-5745 treatment to those subjects who are still enrolled in Arm B.

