### **Futility Interim Analysis**

The end point of the futility interim analysis is OS. The futility analysis will occur approximately after 95 OS events (33.3% of the information relative to the final analysis) have been observed in the ITT population. The analysis will perform a stratified log-rank test for OS in the ITT population. A non-binding futility rule will be implemented. Based on the analysis results, the DMC may recommend terminating the study for lack of efficacy if the predictive power (PP) on OS in ITT population is < 14%. Otherwise, the study will be continued.

Predictive power is defined as a weighted average of the conditional power; the weighting function is determined by the sampling distribution of the observed hazard ratio based on the data at the interim analysis {Lan 2012}. When exactly 95 OS events are observed at the interim, this futility rule of PP <14% corresponds to observing an OS hazard ratio (HR) > 0.95 in the ITT population.

Appendix Figure 1 presents the operating characteristics of futility rule at the interim of 95 OS events with futility boundary of 0.95. When the true hazard ratio is 0.7, the probability of terminating the study early is 7%. On the other hand, when the true hazard ratio is 1, indicating lack of efficacy, the probability of terminating the study early is 60%.

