## 2.2. Final Analysis

The final analysis for the primary endpoint will be conducted after approximately 286 OS events have occurred. Once all outstanding data queries have been resolved, the database will be locked, the blind will be broken, and the efficacy analysis of the study will be performed.

At the final analysis, the type I error rate for testing OS will be controlled by the alpha spending function with O'Brien-Fleming type boundaries. The OS event point will be tested at a one-sided alpha level of 0.023 at 286 OS events. The actual significance levels used will be adjusted based on the actual number of overall events that occur. If the OS endpoint is rejected, the PFS endpoint will be tested at a one-sided alpha level of 0.016. If the PFS endpoint is also rejected, the ORR endpoint will be tested at a one-sided alpha level of 0.016. The actual significance levels used will be adjusted based on the actual number of OS events that occur.

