#### **Futility Interim Analysis**

The end point of the futility interim analysis is OS. The futility analysis will occur approximately after 95 OS events (33.3% of the information relative to the final analysis) have been observed in the ITT population. The analysis will perform a stratified log-rank test for OS in the ITT population. A non-binding futility rule will be implemented. Based on the analysis results, the IDMC may recommend terminating the study for lack of efficacy if the predictive power (PP) on OS in ITT population is  $< 14\%$ . Otherwise, the study will be continued.

Predictive power is defined as a weighted average of the conditional power; the weighting function is determined by the sampling distribution of the observed hazard ratio based on the data at the interim analysis {[Lan 2012](#)}. When exactly 95 OS events are observed at the interim, this futility rule of  $PP < 14\%$  corresponds to observing an OS hazard ratio (HR)  $> 0.95$  in the ITT population.

[Appendix Figure 1](#) presents the operating characteristics of futility rule at the interim of 95 OS events with futility boundary of 0.95. When the true hazard ratio is 0.7, the probability of terminating the study early is 7%. On the other hand, when the true hazard ratio is 1, indicating lack of efficacy, the probability of terminating the study early is 60%.

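### SAP Appendix 4 computes futility predictive power against 1.960, but the planned final OS boundary is 1.993, so predictive power is overstated by about 0.5 percentage points

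*SAP*

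**What the plan says.** SAP Appendix 4 gives a closed-form PP for the futility look. It sets alpha = 0.05, states that this "is the Type I error of the final analysis", and uses the normal quantile at alpha/2. The sample SAS code hard-codes the same value, in a call that begins "quantile('normal', 0.025". The appendix also says that the estimate in the formula "is the observed log HR (treatment arm vs. placebo) at futility interim", although the formula then takes its logarithm.

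Elsewhere the final test is described differently. SAP section 2.2 says: "The OS event point will be tested at a one-sided alpha level of 0.023 at 286 OS events". SAP Table 2-1 repeats that level, and SAP Appendix 3 uses the 0.023 quantile for the final OS boundary. Protocol Table 8-1 gives the Z values: the interim row reads "191 (66.7%) 2.509 0.006" and the final row "286 (100%) 1.993 0.023".

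On timing, SAP Appendix 3 says: "The futility analysis will occur approximately after 95 OS events (33.3% of the information relative to the final analysis". Protocol Appendix 6 adds that, with exactly 95 deaths, "this futility rule of PP <14% corresponds to observing an OS hazard ratio (HR) > 0.95 in the ITT population". Both appendices give the probability of stopping as 7% at a true hazard ratio of 0.7 and 60% at a true hazard ratio of 1. SAP section 2.1 makes the rule non-binding and spends no alpha on it.

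**The concern.** Both documents define PP as a weighted average of conditional power. Conditional power needs the criterion that will be applied at the end of the trial. A final Z between 1.960 and 1.993 fails the plan's final OS test, yet Appendix 4 counts it as a success. The description of alpha is also wrong: 0.05 two-sided is the level for the whole OS testing scheme, not for the final analysis. Neither document says that 1.960 was chosen as a simplification.

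PP below 14% is the only quantitative futility criterion given to the monitoring committee. The statistic should therefore measure what its name says, and Appendix 4 should agree with the boundary used in Appendix 3 of the same SAP.

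**Working it through.** **Inputs.** Deaths at the futility look d1 = 95 (SAP Appendix 3); deaths at the final analysis d = 286 (SAP Appendix 4); 1:1 allocation, which gives the factor 4; critical value c = 1.960 as coded, or 1.993 from Protocol Table 8-1; PP threshold 14%.

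**Boundary check.** Recomputing the Lan-DeMets O'Brien-Fleming-type boundaries at information fraction 0.667 and one-sided 0.025 gives 2.509 and 1.993, as in Table 8-1. The one-sided p-value for 1.993 is 0.0231.

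**Formula (SAP Appendix 4, with HR as the observed hazard ratio).**

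PP = Φ( −c·√(d1/(d − d1)) − √(d·d1/(4(d − d1)))·ln HR )

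With d − d1 = 191:
- √(95/191) = 0.7052
- √(286 × 95/(4 × 191)) = 5.963
- ln 0.95 = −0.0513, so the second term is +0.3059

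**The plan's own figures, c = 1.960.**
- PP at HR 0.95 = Φ(−1.3823 + 0.3059) = Φ(−1.0764) = 14.09%.
- PP = 14% requires the argument to equal −1.0803, so ln HR = (1.0803 − 1.3823)/5.963 = −0.0506 and HR = 0.9506. This reproduces the stated 0.95.
- With SE(log HR) = 2/√95 = 0.2052, a cut at 0.95 stops with probability 59.9% at true HR 1 and 6.8% at true HR 0.70. These match the stated 60% and 7%.

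**Against the planned final boundary, c = 1.993.**
- PP at HR 0.95 = Φ(−1.4056 + 0.3059) = Φ(−1.0997) = 13.57%.
- PP = 14% gives ln HR = (1.0803 − 1.4056)/5.963 = −0.0545 and HR = 0.9469.

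| | c = 1.960 | c = 1.993 |
|---|---|---|
| PP at HR 0.95 | 14.09% | 13.57% |
| HR at which PP = 14% | 0.9506 | 0.9469 |
| Stopping probability at that cut, true HR 1 | 59.7% | 60.5% |
| Stopping probability at that cut, true HR 0.70 | 6.8% | 7.0% |

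**Does the remaining efficacy look account for the difference?** The flat-prior predictive probability of crossing either remaining boundary (2.509 at 191 deaths or 1.993 at 286) is 13.62% at HR 0.95, with a 14% cut at 0.9472. Crediting a win at the efficacy interim does not bring PP back to 14.09%.

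**How often it matters.** The two constants lead to different decisions only for an observed HR between 0.947 and 0.951. From the table (before rounding), the chance of landing there is about 0.7% at true HR 1 and 0.3% at true HR 0.70.

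**The case against.** The strongest reply is that the plan's futility figures agree with each other. Under 1.960, the 14% threshold, the 0.95 cut and the 60% and 7% stopping probabilities all reproduce. At a fixed event count PP is a monotone function of the observed hazard ratio. The 14% can therefore be read as a calibrated cut whose operating characteristics are what count, and those barely move. All of this stands, and it is why the point is minor. It does not make alpha = 0.05 the level of the final analysis.

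A reader might infer more: that at an observed hazard ratio of 0.95 the coded rule says continue while the proper one says stop, so the committee would be given the wrong answer. The documents do not support that as a finding. The hazard ratio of 0.95 is itself the rounded cut, and 13.57% still rounds to 14%, as 0.947 rounds to 0.95. The look is also planned at approximately 95 deaths. With the SAP formula unchanged, PP at 0.95 is 14.28% with 94 deaths, 13.90% with 96 and 13.52% with 98. One extra death crosses 14% without any change of constant, and three shift PP by about as much as the constant does.

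A reader might also take the log hazard ratio wording as a computational fault. Read literally, the formula is undefined for hazard ratios below 1, but the SAS code takes the log of the hazard ratio itself. It is a clerical slip.

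**Conclusion.** The point holds as a wrong constant and a wrong description of alpha in SAP Appendix 4, with a small effect. PP is overstated by about 0.5 percentage points at the stated cut, and the hazard ratio equivalent of 14% is 0.947 rather than 0.951. The stated 0.95, 60% and 7% are right to rounding under either constant.

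It would be a mistake to infer any inflation of type I error. The rule is non-binding, no alpha is spent at the futility look, and the efficacy boundaries are correctly derived. Sample size and efficacy claims are untouched.

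The figures assume 95 and 286 deaths, a log hazard ratio variance of 4 divided by the number of deaths, and the planned boundary of 1.993. Using the quantile of the rounded level 0.023 (1.995) instead gives 13.54% at a hazard ratio of 0.95.

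**What to change.** In the SAP Appendix 4 formula and SAS code, replace the 0.025 quantile with the planned final OS boundary, −1.993. Describe alpha there as the final-analysis level, one-sided 0.023. Then make the equivalence match, in SAP Appendix 3 and Protocol Appendix 6: either PP below 14% corresponds to an observed hazard ratio above about 0.947 at 95 deaths, or keep 0.95 and give the PP threshold as about 13.6%. As a tidy-up, define the estimate in Appendix 4 as the observed hazard ratio.

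The planned boundary is the one to use. A boundary adjusted to the actual number of deaths at the efficacy interim cannot be known at the futility look, because that interim comes later.

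The cost is one constant and a few sentences. The rule stays non-binding and no other analysis changes.

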## Appendix 5. EORTC Scoring Guideline

### Scoring the EORTC QLQ-C30 version 3.0

Table 1: Scoring the QLQ-C30 version 3.0

	Scale	Number of items	Item range*	Version 3.0 Item numbers	Function scales
Global health status / QoL					
Global health status/QoL (revised) †	QL2	2	6	29, 30	
Functional scales					
Physical functioning (revised) †	PF2	5	3	1 to 5	F
Role functioning (revised) †	RF2	2	3	6, 7	F
Emotional functioning	EF	4	3	21 to 24	F
Cognitive functioning	CF	2	3	20, 25	F
Social functioning	SF	2	3	26, 27	F
Symptom scales / items					
Fatigue	FA	3	3	10, 12, 18	
Nausea and vomiting	NV	2	3	14, 15	
Pain	PA	2	3	9, 19	
Dyspnoea	DY	1	3	8	
Insomnia	SL	1	3	11	
Appetite loss	AP	1	3	13	
Constipation	CO	1	3	16	
Diarrhoea	DI	1	3	17	
Financial difficulties	FI	1	3	28	

\* *Item range* is the difference between the possible maximum and the minimum response to individual items; most items take values from 1 to 4, giving *range* = 3.

† (revised) scales are those that have been changed since version 1.0, and their short names are indicated in this manual by a suffix "2" – for example, PF2.

For all scales, the *RawScore*, *RS*, is the mean of the component items:

$$RawScore = RS = (I_1 + I_2 + \dots + I_n) / n$$

Then for **Functional scales**:

$$Score = \left\{ 1 - \frac{(RS - 1)}{range} \right\} \times 100$$

and for **Symptom scales / items** and **Global health status / QoL**:

$$Score = \{(RS - 1) / range\} \times 100$$

**Examples:**

Emotional functioning

$$RawScore = (Q_{21} + Q_{22} + Q_{23} + Q_{24}) / 4$$

$$EF\ Score = \{1 - (RawScore - 1) / 3\} \times 100$$

Fatigue

$$RawScore = (Q_{10} + Q_{12} + Q_{18}) / 3$$

$$FA\ Score = \{(RawScore - 1) / 3\} \times 100$$

**Gastric cancer module: QLQ-STO22**

**Scope**

The gastric cancer module is meant for use among patients with gastric cancer varying in disease stage and treatment modality (i.e. surgery, chemotherapy, radiotherapy, etc.). It should always be complemented by the QLQ-C30.

**Scoring**

	Scale name	Number of items	Item range	QLQ-STO22 item numbers
Functional scales				
Body image	STOBI	1	3	49
Symptom scales				
Dysphagia	STODYS	3	3	31 – 33
Pain	STOPAIN	4	3	34 – 37
Reflux symptoms	STORFX	3	3	38 – 40
Eating restrictions	STOEAT	4	3	41 to 43,46
Anxiety	STOANX	3	3	47,48,50
Dry mouth	STODM	1	3	44
Taste	STOTA	1	3	45
Body image	STOBI	1	3	49
Hair loss	STOHL	2/1	3	51,52*

**Remarks**

- Item 52 is an optional item and depends on the answer to item 51. Item 52 should only be answered and assessed if ‘yes’ has been answered to item 51.
